# 9. SAFETY

Safety analyses will be based on the full analysis set, and the analysis will be conducted according to the actual treatment the subjects receive. No inferential statistics will be performed, and only summary statistics will be provided. Missing safety data will not be imputed.

# 9.1. EXTENT OF EXPOSURE

Exposure to study drug (in days) is calculated as last dose date of study drug – first dose date of study drug + 1. Study drug exposure will be summarized by treatment group.

# 9.2. TREATMENT COMPLIANCE

Study drug compliance (%) is calculated as  $100 \times (total number of capsules dispensed – total number of capsules returned)/exposure of study drug (in days) <math>\times 1 \times 1 \times 10^{-5}$  capsule per day.

Compliance will be summarized by treatment group. In addition, the number and percentage of subjects in pre-specified compliance categories (< 80%, 80-100%, > 100%) will be summarized by treatment group.

## 9.3. ADVERSE EVENTS

Adverse events will be coded using MedDRA to classify events under primary SOC and PT.

A TEAE is defined as an AE that either begins or first recognized after the first dose of study drug or worsens after the first dose of study drug.

The TEAEs below will be summarized by SOC, PT and treatment group. Multiple occurrences of an AE are counted only once per subject per SOC and PT for summary tables.

- Incidence of all TEAEs
- Incidence of all TEAEs by maximum severity (in the following order: severe, moderate and mild) specified by investigators
- Incidence of TEAE by strongest relationship to study drug specified by investigators (in the following order: very likely/certain, probable, possible, unlikely, and unrelated).
- Incidence of serious TEAEs
- Incidence of Serious TEAEs related to study drug specified by Investigators
- Incidence of TEAEs leading to study drug withdrawn

All data collected in the AE case report form (CRF) will be listed in by-subject listings.

# 9.4. LABORATORY EVALUATIONS

If a continuous laboratory value is reported as either below or above the limits of quantification, the qualifiers should be dropped and the numeric value used in the analysis (e.g., "< 3" should be "3" and "> 200" should be "200").

The observed data at each time point and change from baseline at each post-baseline time point in hematology, serum chemistry and quantitative urinalysis test results will be summarized by treatment group.

For hematology, serum chemistry, lipid, cytokine, and creatine phosphokinase, normal ranges for each parameter will be used to categorize the test result as low (value lower than the lower limit), normal (value within the normal range), or high (value higher than the upper limit). Frequency counts and percentages will be presented over time by treatment groups for these categorical data. In addition, shifts from baseline to each post-baseline time point for each parameter will be summarized by treatment group.

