8.4.1.1 General warning

SYN-010 capsules should not be chewed or opened.

The active ingredient of SYN-010 (lovastatin) is currently listed as a pregnancy category X drug and should not be taken during pregnancy. Female subjects who become pregnant must immediately discontinue taking study drug. Subjects will be instructed that known or suspected pregnancy occurring during the study should be confirmed and reported to the investigator, who will then withdraw the female subjects from the study without delay. The investigator should also be notified of any pregnancy occurring during the study but confirmed after completion of the study.

Clinical studies with the commercially-available cholesterol-lowering lovastatin formulation Mevacor[®] (Merck) showed that lovastatin, like other inhibitors of HMG-CoA reductase, occasionally causes myopathy manifested as muscle pain, tenderness or weakness with creatine kinase (CK) above ten times the upper limit of normal. Myopathy sometimes takes the form of rhabdomyolysis with or without acute renal failure secondary to myoglobinuria, and rare fatalities have occurred. The risk of myopathy is increased by high levels of HMG-CoA reductase inhibitory activity in plasma. SYN-010 is designed to limit systemic exposure of HMG-CoA reductase inhibiting lovastatin species and no myopathy or rhabdomyolysis were observed in Phase 1 or Phase 2a clinical trials with up to 12 weeks of SYN-010 42 mg dosing. Transient and reversible increases in serum CK were observed in two subjects treated with SYN-010 42 mg for 8 weeks in the Phase 2a clinical trial; however, these were deemed unrelated to study drug by the investigator and returned to normal without discontinuation of SYN-010.

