9.1 Schedule of assessments

Table 1: Schedule of assessments

X = required; O = only if directed by symptoms or reported AE; ET = early termination

Visit No.	1		2	3	4	5	EOS
Туре	Screen	Pre-treatment	Randomize				Call/Visit
Days	-17 to -14	-17 to -1	1	28	56	84 or ET	85
Window (Days)				±5	±5	±5	+1
Participant Information							
Informed Consent ¹	Х						
Inclusion/Exclusion ¹	Х						
IBS-C Criteria (ROME IV) ¹	Х						
Demographics ²	Х						
Medical History ³	Х		х				
Prior/Concomitant Medications	х		х	х	х	х	х
Diary compliance/ eligibility to randomize ⁴		х	х				
Physical							
Physical Exam ⁵	Х		Х	0	0	Х	0
Vital Signs ⁶	Х		Х	Х	Х	Х	0
12-Lead ECG ⁷	Х					Х	
Drug Dispensing							
Drug Dispensing			х	Х	Х		
Accountability/Returns				Х	Х	Х	
Adverse Events							
AEs			Х	Х	Х	Х	Х
Blood Samples							
Clinical Chemistry (CMP)	Х		Х	Х		Х	
Lipid Panel			Х			Х	
Cytokine Analysis			Х	Х		Х	
Hematology	Х					Х	
Serum Pregnancy ⁸	Х						
Creatine Kinase (CK)	Х			0	0	0	0
Urine Samples							

Urine Drug Screen	Х						
Urine Pregnancy ⁸			Х	Х	Х	Х	
Patient Reported							
Outcomes (REDCap)							
Diary Dispensing or	v					v	
Return ⁹	^					^	
Diary Compliance ¹⁰		Х	Х	Х	Х	Х	
EQ-5D-5L QoL			×			v	
Questionnaire ¹¹			^			^	
Stool Samples ¹²							
Bacteria (16S rRNA)			Х			Х	
Methanogens (qPCR)			Х			Х	
Breath Gases							
Lactulose breath test ¹³	Х					Х	
Single-point breath test			Х	Х	Х		

¹Informed consent, inclusion/exclusion criteria, and ROME IV may be reviewed and signed prior to Visit 1.

²Date of birth, gender, race/ethnicity.

³Patients will complete the information in the REDCap system during the Screening Period.

⁴Patients will be eligible for randomization if they fully respond to the PRO questions on at least 11 of 14 days.

⁵General examination, including head, ears, eyes, nose, throat, endocrine, cardiovascular, respiratory, abdomen, skin, neurological, extremities, and musculoskeletal features.

⁶Body weight, blood pressure (requires the patient to be semi-supine for at least 5 minutes prior to the test) height (Screening Visit only), radial pulse rate, respiratory rate, and temperature.

⁷12-lead ECG requires the participant to be supine for at least 5 minutes prior to the test.

⁸All female participants of child-bearing potential.

⁹Provide and train the patient to use the REDCap system with questionnaire.

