9.3.6 Blood draw

Blood will be drawn by a trained research nurse and collected for hematology, clinical chemistry, lipid, cytokine, and creatine phosphokinase. Laboratory analyses will be performed in the central clinical laboratory and MAST research laboratory at Cedars-Sinai Medical Center. Reference ranges will be supplied by the clinical laboratory and used by the investigator to assess the laboratory results for clinical significance and pathological changes. Blood samples will be used for serum pregnancy tests in women of childbearing potential.

Clinical chemistry (CMP) will be assessed on Visits 1 (Screening Visit), 2, 3, and 5. Creatine kinase (CK) will be assessed during Visit 1, however may be assessed as needed during the remaining study visits as indicated by the development of symptoms suggestive of myopathy and/or rhabdomyolysis.

Blood will be drawn during all visits except Visit 4 and the End-of-Study Call/Visit; however, blood may be drawn on Visit 4 and/or the End-of-Study Call/Visit as dictated by occurrence of subject symptom or adverse events.

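### SAP 9.4 plans creatine kinase (CK) percentages and shifts by visit and arm, but CK after Screening is measured only when symptoms or an adverse event prompt it, and no denominator is set

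*SAP*

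**What the plan says.** SAP 9.4 treats CK like the other laboratory panels: "For hematology, serum chemistry, lipid, cytokine, and creatine phosphokinase, normal ranges for each parameter will be used" to class each result as low, normal or high. It then says "Frequency counts and percentages will be presented over time by treatment groups for these categorical data", and that "shifts from baseline to each post-baseline time point for each parameter will be summarized by treatment group".

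The protocol collects CK differently. Section 9.3.6 says "Creatine kinase (CK) will be assessed during Visit 1", and that it "may be assessed as needed during the remaining study visits as indicated by the development of symptoms suggestive of myopathy and/or rhabdomyolysis". In the schedule of assessments (Protocol 9.1), CK has its own row: X at Screening, nothing at Randomization, and O at Days 28, 56, 84/ET and end of study. The legend reads "X = required; O = only if directed by symptoms or reported AE; ET = early termination".

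SAP 9 adds that missing safety data are not imputed and that safety summaries are descriptive. No section of the SAP gives a denominator for CK or a rule for tests done only on indication.

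**The concern.** A by-visit percentage of high CK, shown by arm beside hematology and chemistry, will be read as the share of that arm with raised CK at that visit. The data cannot support that reading. Patients with a post-baseline CK are there because something happened to them after randomization, and the rest have no value.

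Muscle toxicity is a class risk that Protocol 8.4.1.1 describes at length, and safety is a secondary objective (Protocol 4.2). The same section reports from Phase 2a that "Transient and reversible increases in serum CK were observed in two subjects treated with SYN-010 42 mg for 8 weeks". It goes on to say that the investigator judged these rises unrelated to study drug and that they resolved without stopping it, so this shows interest in the marker rather than an established effect. A display that can be misread in either direction is a poor way to report it.

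**Working it through.** The plan states no CK figure to reproduce. The check has two parts.

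**1. Planned tables against planned data.** Required (X) measurements in the Protocol 9.1 schedule, for the five groups named in SAP 9.4:

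| Group | Required at | Required after first dose? |
|---|---|---|
| Clinical chemistry | Screening, Randomization, Day 28, Day 84/ET | Yes |
| Hematology | Screening, Day 84/ET | Yes |
| Lipids | Randomization, Day 84/ET | Yes |
| Cytokines | Randomization, Day 28, Day 84/ET | Yes |
| CK | Screening | No |

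CK is the only one of the five with no required post-dose value. A shift needs a post-baseline value, so unless a not-tested category is added, the CK shift table can contain only patients tested on indication.

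The visit windows in SAP 6.3 add a smaller problem. Unscheduled results are mapped to the nearest visit window, with Days 2 to 42 assigned to Day 28, and scheduled-visit data take precedence. A CK prompted by symptoms on Day 20 would appear under Day 28. If CK was repeated at the scheduled visit, the repeat would be the analysed record.

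**2. What each denominator estimates.** Let s be the share of an arm tested, a the probability of high CK in tested patients, and b the probability in untested patients.

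- True share with high CK: s·a + (1 − s)·b
- Tested-only percentage: a
- Full-arm percentage (untested counted as not high): s·a

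Hence tested-only minus true = (1 − s)(a − b), which is positive whenever a > b. True minus full-arm = (1 − s)·b, which is never negative.

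The documents give none of s, a or b. The values below are assumptions, with 50 per arm from Protocol 7.1.

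- *Counts.* 2 high of 6 tested in an arm of 50: 2/6 = 33% or 2/50 = 4%.
- *One scenario.* s = 10% (5 tested), a = 30%, b = 5%: true = 0.10 × 0.30 + 0.90 × 0.05 = 7.5%; tested-only = 30%; full-arm = 0.10 × 0.30 = 3.0%.
- *Range.* s from 2% to 20%, with (a, b) set to (30%, 5%), (30%, 10%) or (50%, 5%): true 5.5% to 14%; tested-only 30% to 50%; full-arm 0.6% to 10%.
- *CK unrelated to testing.* a = b = 10%: the tested-only percentage is unbiased at 10%. The full-arm percentage is 0.2% with 2% tested and 2% with 20% tested, so two arms with the same true rate would look different only because testing differed.
- *Precision.* 1 high of 5 tested is 20% (exact 95% CI 0.5% to 72%). 1 high of 2 tested is 50% (1.3% to 99%).

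**The case against.** Several points on the other side stand.

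- **The denominator is open.** A reader might infer that the SAP commits to the tested-only percentage and will overstate raised CK about eightfold (33% against 4%). The SAP does not say so; a full-arm denominator would print 4%. Nor is 4% the correct rate, since it counts 44 untested patients as not high.
- **Different selection by arm is not shown.** In a double-blind trial it is possible, but the documents do not establish it.
- **The testing trigger is wider than muscle symptoms.** Protocol 9.3.6 names those, but the schedule legend also admits a reported adverse event. The subset is event-selected either way.
- **Other outputs limit the harm.** SAP 6.1 already provides by-subject listings. SAP 9.4 prints counts with percentages, so a very small number tested may be visible. Abnormal laboratory findings fall within the adverse event definition (Protocol 9.3.11.1), and SAP 9.3 tabulates treatment-emergent events by arm. The study-level safety trigger in Protocol 9.3.13 refers to enrolled subjects and does not draw on this table. No inferential safety test is planned.
- **The SAP may simply be out of date.** It is based on Protocol Version 3.0, and the protocol reviewed is Version 8.0. The CK schedule in Version 3.0 is not visible. This might explain the mismatch but does not remove it.

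One defence fails. Appendix 13.1 lists CK in its clinical chemistry column, which might suggest that CK is drawn at every chemistry visit. But the schedule gives CK a separate row, and section 9.3.6 separates it from the chemistry panel.

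**Conclusion.** The mismatch is real and minor. SAP 9.4 specifies by-visit percentages and shifts for a test that the protocol does not require after Screening, and it sets no denominator. Neither available denominator gives the incidence of raised CK: the full-arm percentage is too low whenever any untested patient has high CK, and the tested-only percentage is too high whenever tested patients are more likely to have it.

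The 33% and 4% show only how far the printed figure can move with the denominator; they rest on assumed counts. The documents do not support a claim that the table will overstate risk by a known factor, or that it will rank the arms wrongly. The consequence is a potentially misleading descriptive display for a risk that the protocol itself highlights. No efficacy conclusion or planned test is affected. Whether CK should be measured routinely is a clinical matter and is not judged here.

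**What to change.** In SAP 9.4:

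1. Remove creatine phosphokinase from the by-visit low/normal/high tables and from the shift tables.
2. For each arm, report as counts the number treated, the number with any post-baseline CK test and the number with raised CK. Label any percentage of treated patients as event-detected. Show an arm with nobody tested as not tested rather than 0%.
3. Add the reason for testing to the existing by-subject listing.
4. State that CK change in untested patients is not estimated.

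The cost is SAP wording and one table shell. No additional tests are needed. The reason for testing is the only new listing item.

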# 9.5. VITAL SIGNS AND 24-HOUR AMBULATORY BLOOD PRESSURE

Observed data at each time point and the change from baseline at each post-baseline time point for vital signs will be summarized by treatment group.

# 9.6. ECG

Observed data at each time point and the change from baseline at Week 12 in ECG parameters (HR, RR, PR, QRS, and QTcF) will be summarized by treatment group.

The number and percentage of subjects with QT and QT corrected with Fridericia's formula (QTcF) values falling into the following categories at Week 12 will be summarized by treatment group:

- Change from baseline of 30 60 msec in QT and QTcF.
- Change from baseline of > 60 msec in QT and QTcF
- Week 12 value > 450 and baseline <= 450 msec in QT and QTcF
- Week 12 value > 500 and baseline <= 500 msec in QT and QTcF

QTcF (msec) is calculated as: QT (msec)/  $RR^{1/3}$ , where RR = 60 / heart rate (bpm).

The number and percentage of subjects with other clinically significant ECG findings and rhythm findings will also be summarized at Week 12 by treatment group.

## 9.7. RESCUE MEDICATION

The number and percentage of subjects using protocol-specified rescue medication at any time post-baseline will be summarized by treatment.

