8.8 Prior and concomitant therapy

Any prior or concomitant therapy that the patient may be taking and may be necessary for the patient's welfare taken within two weeks prior to the start of the study and during the study must be recorded in the patient's source documentation and in the CRF (including start/stop dates, dose frequency, route of administration, and indication).

The patient may be on a stable, continuous regimen of fiber, or probiotics one month before the Screening Visit; however, he/she must maintain a stable dose regimen through Week 12. Additionally, certain drugs used for the treatment of IBS (e.g. low dose tricyclic antidepressants) may be allowed at the discretion of the Medical Monitor provided the patient remains on a stable dose for one month prior to the Screening Visit and throughout the study with the exception of tegaserod, lubiprostone, linaclotide, metoclopramide, prucalopride, domperidone, plecanatide, CandiBactin, Atrantil, Allimax/Allimed within 2 weeks prior to the Screening Visit or antibiotics within 2 months prior to the Screening Visit.

Rescue medication will be allowed for severe constipation (i.e. when symptoms become intolerable). For guidance purposes for this protocol, intolerable symptoms may be when a subject has not had a complete spontaneous bowel movement (CSBM) in the preceding three days with an abdominal pain score of \geq 6 on an 11-point (0-10) scale each day during that time period. However, intolerability is ultimately a subjective judgment, and principal investigators and their patients make the final decision regarding what is intolerable and requires use of the rescue medication. For the Randomization Visit only, rescue medication will not be allowed the day before, the day of, or the calendar day after the Randomization Visit. If rescue medication is taken during this time, it must be recorded as a protocol deviation and the subject should not be randomized. The use of protocol-specified rescue medication and non-protocol-specified laxatives will be recorded in the subject record.

Permitted rescue medications include bisacodyl, magnesium citrate, magnesium hydroxide, and lactulose. Dosage and frequency should be followed according to package insert on rescue medication and should not exceed recommended doses as approved by package insert.

9. Procedures and variables

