9.3.10 Breath gases

9.3.10.1 Lactulose breath test

Lactulose breath tests will be performed during the Screening Visit and Visit 5. Subjects will be asked to undergo a 24-hour preparatory period just prior to the test. Subjects will maintain a bland diet during the first 12 hours and fast during the remaining 12. A baseline breath test will be collected by exhaling into disposable collection bag with a volume of 750 mL. Following the baseline breath sample, subjects will consume 10 g lactulose dissolved in water. Subsequent breath samples will be collected every 15 minutes over the remainder of the 120-minute test. Breath samples will be analyzed for hydrogen, methane, carbon dioxide, and hydrogen sulfide levels immediately after collection via gas chromatograph. The gas chromatograph will be used as approved.

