13.3 Daily questionnaire

Did you have a bowel movement today?

If yes, did it feel complete?

What did it look like? Please use the Bristol Stool Chart as a reference.

Did you have more than one bowel movement today?

If yes, did it feel complete?

What did it look like?

Did you have more than two bowel movements today?

If yes, did it feel complete?

What did it look like?

Did you take a laxative today?

Date: June 30. 2020	Version: 8.0	Page: 46 of 52

If yes, please specify: Protocol-recommended rescue medication (bisacodyl, magnesium citrate, magnesium hydroxide, or lactulose) or Other laxative (oral, suppository, or enema)

If other, please specify the name of the laxative taken.

How severe has straining been during your bowel movements over the last 24 hours.

- 0 None (absent)
- 1 Mild (not very severe)
- 2 Moderate (somewhat severe)
- 3 Severe
- 4 Very Severe

Using the scale above, please rate the worst level of abdominal pain you have felt over the past 24 hours.

Bloating is a condition in which the belly (abdomen) feels full and tight or may look or feel swollen/distended. Patients may experience abdominal fullness, pressure, or a sensation of trapped gas.

Please rate the worst level of bloating you have felt over the last 24 hours.

- 0 None (absent)
- 1 Mild (not very severe)
- 2 Moderate (somewhat severe)
- 3 Severe
- 4 Very Severe

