#### 3. ENDPOINTS

#### 3.1. PRIMARY EFFICACY ENDPOINT

The primary efficacy endpoint is the change from baseline in the weekly average number of complete spontaneous bowel movements [CSBMs] during the 12-week Treatment Period.

A CSBM is a spontaneous bowel movement [SBM] that is associated with a sense of complete evacuation. An SBM is a bowel movement that occurs in the absence of rescue medicine use or other laxative use (e.g. suppository or enema) on the calendar day of bowel movement or the calendar day before the bowel movement.

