# 8.2. SECONDARY AND EXPLORATORY EFFICACY ENDPOINTS AND ANALYSIS

# 8.2.1. Secondary Efficacy Endpoints

The secondary efficacy endpoints are listed below:

- The proportion of overall responders during the 12-week Treatment Period (overall 12-week responders).
- Proportion of overall stool frequency responders during the 12-week Treatment Period.
- Proportion of overall abdominal pain intensity responders during the 12-week Treatment Period.
- Proportion of overall bloating responders during the 12-week Treatment Period.

• Proportion of patients using rescue medication.

The comparisons of the proportions will be performed using the Chi-squared test for equal proportions based on the full analysis set. The Chi-squared test from SAS Proc Freq will be used for the comparison of the treatment differences (each SYN-010 dose group versus placebo). Nominal P-values and 95% Newcombe-Wilson CIs for treatment differences will be presented.

To control the overall false positive rate, a fixed sequence testing procedure will be used for the testing of the secondary endpoints listed above. Specifically, the secondary endpoints will be tested formally if statistical significance is achieved for the primary endpoint for both dose groups, otherwise, the secondary endpoints will not be tested formally. If statistical significance is achieved for the primary endpoint for both dose groups, then the secondary endpoints will be tested formally in the order of the list for the 42 mg dose. The first listed secondary endpoint will be tested at the 2-sided alpha = 0.05 level. If statistical significance is not achieved, then the testing procedure will stop. If statistical significance is achieved for the first listed secondary endpoint, then the following secondary endpoint will be tested at the 2-sided alpha = 0.05 level. The testing procedure will continue for the testing of the secondary endpoints until statistical significance is not achieved for a secondary endpoint for the 42 mg dose group. If statistical significance is achieved for all listed secondary endpoints of the 42 mg dose group, then the testing procedure will be repeated for the 21 mg dose group.

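### The SAP's only counting rule for rescue use can count the Visit 5 breath-test lactulose as rescue, because nothing excludes the test dose

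*SAP*

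**What the plan says.** SAP 8.2.1 lists "Proportion of patients using rescue medication" as the last of five secondary endpoints. Each dose is compared with placebo by a chi-squared test on the full analysis set, at two-sided 0.05 within a fixed sequence. Neither 3.2 nor 8.2.1 states which products, which period or which data source make a patient a user. The only counting rule is in SAP 9.7: "The number and percentage of subjects using protocol-specified rescue medication at any time post-baseline will be summarized by treatment".

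Protocol 8.8 gives the list: "Permitted rescue medications include bisacodyl, magnesium citrate, magnesium hydroxide, and lactulose". It also gives the purpose: "Rescue medication will be allowed for severe constipation (i.e. when symptoms become intolerable".

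Protocol 9.3.10.1 uses one of those drugs as a test substrate. "Lactulose breath tests will be performed during the Screening Visit and Visit 5", and "Following the baseline breath sample, subjects will consume 10 g lactulose dissolved in water". Table 1 places that visit at Day 84 or early termination, with a window of 5 days either side.

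The daily questionnaire in Protocol 13.3 asks whether a laxative was taken that day and splits a yes into "Protocol-recommended rescue medication (bisacodyl, magnesium citrate, magnesium hydroxide, or lactulose) or Other laxative (oral, suppository, or enema". It has no instruction about the breath-test drink.

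The spontaneous bowel movement (SBM) definition in SAP 3.1 uses both categories. A movement is not spontaneous if there was rescue use "or other laxative use (e.g. suppository or enema) on the calendar day of bowel movement" or on the calendar day before.

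**The concern.** One substance has two roles, and the counting rule does not separate them. A patient who needed no rescue in 12 weeks, drinks the test lactulose and answers the diary literally meets the 9.7 rule as a rescue user. Because the test is scheduled in every arm, such false users add to both sides of each comparison and shrink the difference.

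This reaches beyond one endpoint. Under SAP 8.2.1 the 21 mg secondary endpoints are tested formally only after all five have succeeded for 42 mg, so a diluted 42 mg rescue result would close off every formal 21 mg secondary test. Protocol 6.6 instead follows the list in 4.2, where rescue use stands ahead of the overall responder endpoint.

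There is a smaller side effect on the bowel-movement counts. Movements on the test day or the next day are scored as spontaneous or not according to whether the patient logged the test dose.

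**Working it through.** **The plan's own figure.** The documents give no rescue rate and no power for this endpoint. Their one design figure is 90% power for the primary endpoint (Protocol 6.8, SAP 2.2): difference 1.5 − 0.5 = 1.0, SD 1.5, 50 per group, two-sided 0.05. A noncentral t calculation gives 91.0%, so it reproduces. It does not bear on rescue use beyond supplying n = 50 per arm.

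**The chain in the text.**
1. Lactulose is on the rescue list (Protocol 8.8, 13.3).
2. Every patient is scheduled to take it at Visit 5 or early termination (Protocol 9.3.10.1, Table 1). The Screening test comes before baseline and does not matter here.
3. The diary captures any laxative that day and pre-prints lactulose as protocol rescue.
4. SAP 9.7 counts listed rescue at any time after baseline. It does not require use for constipation and does not exclude the test.

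**Illustration of size.** Let p be the true rate of rescue use. Let f be the share of patients not otherwise counted whose test dose is logged as rescue, equal in all arms. Then

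counted rate = p + (1 − p)f, and counted difference = (true difference)(1 − f).

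Example for f = 25%: placebo 0.40 + 0.60 × 0.25 = 0.55; active 0.20 + 0.80 × 0.25 = 0.40; difference 0.20 × 0.75 = 0.15.

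Power is the normal approximation for two proportions, Φ[(Δ − 1.96·SE0)/SE1], with SE0 from the pooled rate and SE1 from the separate rates. At f = 0: SE0 = √(2 × 0.30 × 0.70/50) = 0.0917 and SE1 = √((0.24 + 0.16)/50) = 0.0894, so Φ[(0.20 − 0.1796)/0.0894] = Φ(0.228) = 59%.

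All true rates and all values of f are assumptions.

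| f | Counted rates, true 40% v 20% | Difference (points) | Power | Power, true 30% v 15% | Power, true 50% v 25% |
|---|---|---|---|---|---|
| 0 | 40% v 20% | 20 | 59% | 43% | 74% |
| 10% | 46% v 28% | 18 | 46% | 31% | 62% |
| 25% | 55% v 40% | 15 | 32% | 20% | 47% |
| 50% | 70% v 60% | 10 | 18% | 12% | 27% |

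**Bowel-movement counts.** The Visit 5 window is Days 79 to 89, which is 11 days. SAP 6.3 does not define diary weeks. If Week 12 is Days 78 to 84, then 6 of the 11 permitted days (79 to 84) fall inside it. One movement scored differently changes that week's count by about 1 and the 12-week mean by about 1/12 = 0.08 per week, against the planned difference of 1.0 and SD of 1.5.

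**The case against.** Four points on the other side have weight.

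- **SAP 9.7 is a safety summary.** Section 9 is analysed by actual treatment and without inference, and 8.2.1 does not refer to it. Applying 9.7 to the tested endpoint is therefore an inference. This stands. The alternative, though, is that the tested endpoint has no definition of use at all, which calls for the same repair.
- **The over-count may be rare.** Protocol 8.8 ties rescue to severe constipation, so a test drink is not rescue in that sense. The patient would have to regard it as a laxative and tick the rescue category, and the diary review at Visit 5 would have to let it pass. Table 1 also places diary return at Visit 5, and the documents do not say that an entry is made after the test. If none is, SAP 6.4 sets the unanswered item to no use. This stands as a limit on frequency, but it does not change what the rule would count.
- **Low position and low power.** Rescue use is formally tested for 42 mg only after the primary endpoint succeeds for both doses and four responder endpoints succeed. Even without error, the illustration gives only 59% power. This limits the consequence, although the 21 mg secondary tests still depend on it.
- **The bowel-movement effect is tiny and occurs in all arms.** This stands.

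A reader might go further and infer that leaving out unlisted laxatives is an error too, so that patients are misclassified in both directions. The documents do not support that. Protocol 8.8, Protocol 13.3 and SAP 3.1 all keep rescue medication and other laxatives as separate categories, so counting listed products only matches the endpoint as named. Nor do they show that such a count would favour placebo, since no rates of unlisted use are given.

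**Conclusion.** The point holds as a gap in the definition with a possible over-count, not as a demonstrated misclassification. The literal rule can count breath-test lactulose as rescue use, and no section of either document excludes it. If that happens at the same rate in all arms, it shrinks the difference in proportion to the share logging the test dose. The loss is 13 points of power at a 10% share and 27 points at 25%, under assumed true rates of 40% and 20% with 50 per arm. The true rates and the logging share are assumptions, so the table shows how sensitive the endpoint is and does not forecast a result.

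A reader might also infer that the primary result is at risk. The documents do not support that either: about 0.08 movements per week for each affected movement is negligible beside a planned difference of 1.0. The scoring rule still needs to be the same for everyone.

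The change is worth making because it is cheap, agrees with the stated purpose of rescue, and removes an avoidable source of dilution from an endpoint on which other formal tests depend.

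**What to change.** Before any unblinding, amend the SAP as follows.

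1. In 3.2, 8.2.1 and 9.7, define use once: diary-recorded protocol rescue medication after first dose, excluding lactulose given for the Visit 5 or early-termination breath test. Genuine rescue use on that day still counts. The printed questionnaire records the rescue category but asks for a product name only for other laxatives, so resolve a rescue entry on the test date by blinded check against the subject record.
2. State one rule for SBM and CSBM scoring on the test day and the next calendar day, applied to all patients whether or not the test dose was logged. One option is to treat both days as not assessed. Their exclusion must then be explicit, because SAP 6.4 otherwise reads an unanswered day as one with no bowel movement.
3. Add a supportive analysis counting any laxative, listed or other. These products are already recorded and already disqualify an SBM. Do not replace the named endpoint with it.

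The cost is SAP wording, a small amount of extra analysis, and at most two diary days per patient not assessed. Where two other days in that week are already missing, 2 + 2 = 4 exceeds the SAP's limit of three and the week would become missing. The visit date and diary entries are already collected, and no clinical procedure changes.
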